4.6 Safety Variables

The following safety variables will be analyzed for the study: adverse event (including infusion and allergic reactions), vital signs, C-SSRS, laboratory abnormalities, ECG, and MRI safety evaluations.

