3.2 Benefits and Risks

Patients with PSP suffer serious debilitating symptoms that affect gait and balance, vision, swallowing and speaking, and cognition. The disease is characterized by tau aggregation and is ultimately fatal. No approved treatment exists.

ABBV-8E12, a humanized monoclonal antibody that is being developed for the treatment of PSP, may block tau seeds from propagating between cells, and therefore, may slow disease progression, thus providing a viable treatment option for patients with PSP. The safety profile of ABBV-8E12 to date has been favorable, and no clinically relevant patterns of adverse events or abnormal laboratory findings have been observed. Further, no ADAs were detected in postdose samples in an SAD study in subjects with PSP.

Risks include infusion reactions and possibly life-threatening allergic reactions; however, no systemic hypersensitivity or injection site reactions have been reported to date. Subjects will be monitored closely during clinical trials for the occurrence of these events, study drug will be withdrawn immediately in the case of allergic reaction, and appropriate medical therapy will be provided for any adverse event.

Evidence of efficacy demonstrated in preclinical studies and safety data from clinical studies obtained to date provide a strong rationale for continuing the assessment of safety and efficacy of ABBV-8E12. The benefit-risk profile of ABBV-8E12 will be further defined in Study M15-562, which is ongoing, and in Study M15-563, which is described herein.

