Study drug will be infused 3 times during the first 4 weeks: on Days 1, 15, and 29. Subjects who received placebo in Study M15-562 will receive ABBV-8E12 on Day 15 in Study M15-563, and subjects who received ABBV-8E12 in Study M15-562 will receive placebo on Day 15 in Study M15-563 (to maintain the blind in Study M15-562). After Day 29 of Study M15-563, study drug will be administered every 28 days until one of the discontinuation criteria is met, until the study is discontinued by the sponsor, or until the study reaches completion. The rate of infusion for each subject will be based upon that subject's most recently obtained weight and will range from 3.5 to 4.7 mL/min (210 to 282 mL/hr) (refer to Section 5.5.1 for details on infusion rates). Subjects will be observed on-site for at least 30 minutes after the end of study drug infusions.

Study drug will be administered and study procedures will be performed as shown in [Appendix C](#). Safety and tolerability will be monitored throughout the study. Blood samples will be collected for pharmacokinetic and anti-drug antibodies (ADA) assessments every 3 months during the first 6 months, and every 6 months thereafter.

Lumbar puncture will be performed every 6 months during the first year, then once a year thereafter; it is optional every 6 months in years 2 through 5. Volumetric MRI will be performed every 3 months during the first 6 months, then every 6 months thereafter. In a subset of subjects (up to 50) at participating sites, subjects will be assigned digital sensor BioStamp units to be worn for 1 week epochs starting on Day 1, Day 29 (Week 4), Day 57 (Week 8), and Day 85 (Week 12).

A schematic of the study design is shown in Figure 1.

Figure 1. Study Schematic

a. Additional interim analyses may be performed.

DMC Review of Safety Data

A Data Monitoring Committee (DMC) will review unblinded safety data and make recommendations to the Sponsor based on the totality of available clinical data. The DMC memberships, responsibilities, and operating logistics are documented in a DMC charter. The DMC consists of at least 2 external clinicians, at least 1 external statistician, and at least 1 external pharmacokineticist.

The data set reviewed by the DMC will consist of all available safety and pharmacokinetic data in the study, including data from any subjects who have received at least 1 dose of study drug.

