6.1.7.3 Non-Specific Off-Target Toxicities

Potential toxicities resulting from the non-human origin of ABBV-8E12 include allergic reactions or infusion reactions, including anaphylaxis or anaphylactoid reactions, flu-like symptoms, including fever, fatigue or loss of appetite, or rash. ABBV-8E12 is lacking the Fragment Crystallizable (Fc) effector function activity and therefore Fc-mediated antibody-dependent cellular cytotoxicity and complement-dependent cytotoxicity is not expected. In addition, ABBV-8E12 exhibited a favorable in vitro immune-safety profile. No infusion reactions have occurred in the single dose PSP clinical study or in the Expanded Access protocol (Studies C₂N-8E12-EA-001 and C₂N-8E12-DE-003).

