10.2.1 Adverse Event Overview

The number and percentage of subjects experiencing one or more adverse events in the following adverse event categories will be summarized for each treatment group and overall subjects in both Stand-Alone data set and the Cumulative data set. No comparisons of treatment groups will be performed.

- Any TEAE
- Any TEAE that was rated reasonable possibility of being related to study drug by the investigator
- Any severe TEAE
- Any serious TEAE
- Any TEAE that led to discontinuation of study drug
- Any fatal TEAE
- All deaths

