10.2.2 Adverse Event Incidence

TEAE incidence will be summarized and presented using primary MedDRA system organ classes (SOCs) and preferred terms (PTs). The system organ classes will be presented in alphabetical order and the preferred terms will be presented in the alphabetical order within each system organ class. Subjects reporting more than one adverse event for a given MedDRA PT will be counted only once for that term. Subjects reporting more than one adverse event within a SOC will be counted only once for the SOC total. Subjects reporting more than one adverse event will be counted only once in the overall adverse event total.

The number and percentage of subjects experiencing one or more TEAEs will be summarized by PT for each treatment group and overall subjects. The PTs will be presented by decreasing frequency in overall subjects.

The number and percentage of subjects experiencing one or more adverse events in the following adverse event categories will be summarized by primary SOC and PT for each treatment group and overall subjects.

- Any TEAE
- Any serious TEAE
- Any TEAE that led to discontinuation of study drug
- Any TEAE assessed by the investigator to be Reasonable Possibility of Being Related to study drug

The number of subjects experiencing one or more TEAEs will also be summarized by maximum severity category (mild, moderate, severe and unknown) and primary SOC and PT for each treatment group and overall subjects. Subjects reporting more than one TEAE for a given PT will be counted only once for that term in the most severe category reported. If a subject has an adverse event with unknown severity, then the subject will be counted in the severity category of "unknown" even if the subject has another occurrence of the same event with a severity present. The only exception is if the

subject has another occurrence of the same adverse event with the most extreme severity – "Severe." In this case, the subject will be counted under the "Severe" category. No comparisons of treatment groups will be performed.

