Appendix B. Criteria for Potentially Clinically Significant Vital Sign and Weight Values

Vital Signs	Very Low (VL)	Very High (VH)
Systolic Blood Pressure (SBP) (mmHG)	≤ 90 and decreased ≥ 30 from baseline	≥ 180 and increased ≥ 40 from baseline
Diastolic Blood Pressure (DBP) (mmHG)	≤ 50 and decreased ≥ 20 from baseline	≥ 105 and increased ≥ 30 from baseline
Pulse (bpm)	≤ 50 and decreased ≥ 30 from baseline	≥ 100 and increased ≥ 30 from baseline
Temperature (C)	≥ 1.1 decrease from baseline	> 38.5 or increase ≥ 1.1 from baseline
Orthostatic SBP (Hypotension) (mmHg)	Decrease of ≥ 30 in SBP (supine to standing)	NA
Orthostatic DBP (Hypotension) (mmHg)	Decrease of ≥ 20 in DBP (supine to standing)	NA
Weight (kg)	Decreased $\geq 7\%$ from baseline	Increased $\geq 7\%$ from baseline

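### Infusion and allergic reactions are named for analysis in SAP 4.6, but no SAP output gives a grouped count or a per-infusion rate; separately, the high-temperature flag in Appendix B can mark normal readings

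*SAP*

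**What the plan says.** SAP 4.6 (Safety Variables): "The following safety variables will be analyzed for the study: adverse event (including infusion and allergic reactions", followed by vital signs, C-SSRS, laboratory abnormalities, ECG and MRI.

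Protocol 3.2: "Risks include infusion reactions and possibly life-threatening allergic reactions". No other drug risk is named in that section. Protocol 6.1.7.3 says the potential toxicities arising from the antibody's origin "include allergic reactions or infusion reactions, including anaphylaxis or anaphylactoid reactions, flu-like symptoms, including fever, fatigue or loss of appetite, or rash".

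SAP 10.2.2: "TEAE incidence will be summarized and presented using primary MedDRA system organ classes (SOCs) and preferred terms (PTs". Further tables cover serious, related and treatment-ending events, maximum severity and maximum relationship, and SAP 10.2 adds geographical region. The overview in SAP 10.2.1 has the standard rows, such as "Any TEAE that led to discontinuation of study drug". The listings in SAP 10.2.3 cover all, related, serious, treatment-ending and fatal events, and deaths.

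Protocol 5.1, on the second infusion: "subjects who received ABBV-8E12 in Study M15-562 will receive placebo on Day 15 in Study M15-563". Former placebo subjects receive active drug that day. The stated purpose is to protect the parent-study blind, and Protocol 5.5.1 says placebo is given at no other time.

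SAP Appendix B, very high temperature: "> 38.5 or increase ≥ 1.1 from baseline". The blood pressure and pulse rows in the same table require both a level and a change.

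**The concern.** SAP 4.6 names infusion and allergic reactions within the adverse events to be analyzed, but neither term returns in any SAP analysis section. There is no grouped search, no event of special interest and no window relative to an infusion. The interim list in SAP 4.4 has the same structure and leaves further detail to a DMC Charter, which is not among the documents. Protocol 8.1.2.2 does not fill the gap.

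Long-term safety and tolerability is a primary objective, and SAP 9.0 drops formal efficacy analysis, so the safety description carries most of the report. For an antibody infused up to 66 times, a reader will want to know how many subjects had a reaction of this kind and how often per infusion. As written, the reader would have to assemble that count from separate preferred-term rows, choosing the terms after seeing the data.

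The temperature flag is a separate, smaller matter. Because its two conditions are joined by an or, a rise from 35.8 to 36.9 C is reported as very high.

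**Working it through.** The plan gives no event rate, power or sample size figure on this point, so there is none to reproduce beyond the dosing schedule.

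**1. Infusion count.** Doses fall on Days 1, 15 and 29, then every 28 days to Day 1793 (Protocol Appendix C). That is 3 + (1793 − 29)/28 = 3 + 63 = 66, matching the final dose number in Appendix C. Early-start subjects have at most 65 active infusions and 1 saline; delayed-start subjects have at most 66 active. SAP 8.0 already counts doses, so the denominator for a per-infusion rate exists.

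**2. Is a window feasible?** Protocol 6.1 records the date of onset of each event. Protocol 5.5.1 records infusion start and stop to the minute. No clock time of onset is specified, so a same-day or next-day window is possible from the stated data; an hours-based one may not be.

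**3. What grouping adds (illustration only).** Assume 2:1 active to placebo in the parent study and full rollover of 378. One delayed-start arm then has 378/3/2 = 63 subjects. Assume a true grouped rate of 4%.
- One grouped row, P(at least 2 subjects) = 1 − 0.96^63 − 63 × 0.04 × 0.96^62 = 0.72.
- Same events spread evenly over six preferred terms, rate 0.04/6 each: P(at least 2 in a given row) = 0.066. The chance that any of the six rows reaches 2 is about 1 − (1 − 0.066)^6 = 0.34.

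This applies only to reactions recorded as symptoms. Those recorded as a diagnosis do not spread in this way.

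**4. Temperature flag.** Assume baseline and later readings in an afebrile subject are independent normal with common SD σ. With Z standard normal, the chance that at least one of n readings is 1.1 C or more above baseline is 1 − E[Φ(1.1/σ + Z)^n].

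| σ (C) | n = 15 | n = 66 |
|---|---|---|
| 0.20 | 0.07% | 0.25% |
| 0.25 | 1.1% | 3.2% |
| 0.30 | 4.7% | 11.6% |
| 0.35 | 10.9% | 23.5% |
| 0.40 | 18.6% | 35.7% |

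For comparison, with mean 36.6 C and SD 0.4 C, exceeding 38.5 C needs z = 1.9/0.4 = 4.75. That is about 1 in a million per reading, or 0.007% over 66. The requirement in SAP 10.4.2 that a value be more extreme than baseline does not help, since any rise meets it.

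**The case against.** **Reactions are not lost.** SAP 4.6 places these reactions inside the adverse event variable, and SAP 10.2 analyzes all treatment-emergent events, so the sentence can be read as promising nothing separate. Protocol 6.1 asks for a diagnosis where known, Protocol 6.1.3 makes timing part of the causality judgement, and related, severe, serious and treatment-ending events are all tabulated by sequence. This stands. A reader might infer that the reactions go unreported or cannot be counted by sequence at all; the documents do not support that. Protocol 6.1.7.3 can also be read as listing flu-like symptoms and rash beside infusion reactions, not as forms of them, and nothing in the documents shows that these symptoms are common in this population.

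**Not the only risk in the protocol.** Lumbar puncture risks appear in Protocol 5.3.1.1.12, and neurotoxicity is monitored under 6.1.7.5. The claim is limited to the drug risks named in 3.2.

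**Day 15 is not a wasted control.** A reader might see a blinded saline arm going unused. It is a blinding device. Its recipients had 52 weeks of drug plus a dose 14 days earlier. At the 27 to 37 day half-life in Protocol 3.0, about 0.5^(14/27) = 70% to 0.5^(14/37) = 77% of that level remains. The other group is at its second dose. SAP 10.1 also rules out group comparisons. This stands.

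**The window catches other events.** Lumbar puncture is scheduled on Day 1 and at Weeks 24 and 52 but not on Days 15 or 29, and the protocol expects headache after it. Rates would differ between visits for that reason alone. This stands, and the fix has to handle it.

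**Temperature was never an infusion-reaction detector.** Appendix C schedules no post-infusion reading, and Protocol 5.3.1.1.4 and 5.3.1.1.5 put vital signs before blood draws, which at drug-sampling visits include one taken before infusion. Low temperature and weight are also flagged on change alone, and SAP 10.4.2 lists every flagged observation, so readings above 38.5 C can be found. That limits the harm but does not make the summary row right. The figures for 66 readings assume five full years on study, which many subjects with this disease may not reach.

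**Conclusion.** The point holds as a reporting gap. The SAP names infusion and allergic reactions for analysis and gives no definition, no grouped count and no per-infusion rate. Individual preferred terms, severity, relationship and discontinuation outputs will still show reactions recorded as diagnoses. No claim that a signal would be missed is warranted; the figures of 72% against 7% per row rest on an assumed arm size, rate and even spread.

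The temperature criterion does label ordinary variation as very high. The size depends on an SD that the documents do not give and on independent readings: about 1-19% of afebrile subjects over 15 readings and 3-36% over 66 for SD 0.25 to 0.40 C, and under 0.3% for 0.20 C.

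Both are worth changing before unblinding. Neither affects the conduct of the trial.

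**What to change.** Add to SAP 10.2, before unblinding:

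1. A prespecified list or grouped search of hypersensitivity, anaphylaxis and infusion-reaction terms, tabulated descriptively by treatment sequence, with a subject listing.
2. Treatment-emergent events with onset on an infusion date or the next day, by sequence and by infusion (Day 1, Day 15, Day 29, later), as subjects and as events per 100 infusions. Label Day 15 in early-start subjects as saline, without a contrast. Show visits with a lumbar puncture separately, or exclude procedure-related events.

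In SAP Appendix B, report temperature above 38.5 C and a rise of at least 1.1 C from baseline as two rows.

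The cost is SAP wording and two or three tables from data already collected. The downside is that some events unrelated to the drug will fall inside a date-based window, and a footnote should say so.

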4.7 Pharmacokinetic Variables

The concentration of ABBV-8E12 in serum and CSF samples will be summarized at each collection time point in the study. Data from this study may be combined with data from other ABBV-8E12 studies for pharmacokinetic analyses.

4.8 Biomarker and Pharmacogenetic Research Variables

4.8.1 Biomarker Research Variables

Blood and CSF samples will be collected to conduct research to investigate disease-related and drug-related biomarkers. The biomarkers to be analyzed may include, but are not limited to, the following:

- CSF and Plasma Biomarkers:
 - Tau in CSF and plasma
 - Additional exploratory CSF and plasma-based pharmacodynamic variables for which concentration data are reported
- Imaging Biomarkers:
 - Regional and/or whole brain volume derived from MRI
 - Fractional anisotropy and diffusivity measures in brain regions of interest derived from DTI
- Digital Biomarkers:
 - BioStamp sensor motor outcomes including posture, gait, and step count

4.8.2 Pharmacogenetic Research Variables

Optional samples may be collected to conduct exploratory investigations into known and novel biomarkers. The types of biomarkers to be analyzed may include, but are not limited to, nucleic acids, proteins, lipids or metabolites. The samples may be analyzed as part of a multi-study assessment of factors influencing the subjects' response to the study drug (or drugs of the same or similar class) or the development and progression of the subjects' disease or related conditions. The samples may also be used to develop new diagnostic tests, therapies, research methods or technologies.

If such data are obtained, the results from these analyses would be exploratory in nature and may not be included with the study report. The analysis for such data is not addressed in this SAP.

5.0 Analysis Populations

5.1 Analysis Data Sets

Data Sets for Efficacy Analyses

Two data sets will be created for the efficacy analysis: an intent-to-treat (ITT) data set and a delayed-start data set.

ITT Data Set: the ITT data set consists of all subjects who received any dose of study drug in Study M15-563. All efficacy analyses will be conducted on the ITT data set using data from Study M15-563 alone unless otherwise specified.

Delayed-Start Data Set: The Delayed-Start data set includes all subjects from the Study M15-562 ITT data set who received placebo or ABBV-8E12 in Study M15-562 regardless of whether they enroll in Study M15-563 or not. For the Delayed-Start analysis, efficacy data for PSPRS total score from both Study M15-562 and Study M15-563 studies will be included.

Data Sets for Safety Analyses

The safety data set will consist of all subjects who received any dose of study drug infusion in Study M15-563. For safety analyses, the actual treatment received will be used instead of the treatment assignment at enrollment. There are two safety data sets: a Stand-Alone data set and a Cumulative data set.

Stand-Alone Data Set: The Stand-Alone data set is the primary data set for safety analyses, and will contain data from Study M15-563 only, regardless of the treatment received in Study M15-562. Baseline for the Stand-Alone data set will be the last observation on or before the first dose of ABBV-8E12 in Study M15-563. If no Baseline is recorded in Study M15-563, the last value in Study M15-562 will be used as the Baseline.

Cumulative Data Set: The Cumulative data set will consist of data from both Study M15-562 and Study M15-563. It is the secondary data set for safety analyses. For subjects who were in the placebo group in Study M15-562, their safety data from Study M15-562 will not be included in the Cumulative data set but their safety data from Study M15-563 will be included. For subjects who were in the placebo group in Study M15-562, Baseline will be the last observation prior to the first dose of study drug in Study M15-563. For subjects who were in ABBV-8E12 treatment groups in Study M15-562, Baseline for the Cumulative data set will be their Baseline in Study M15-562.

Data Sets for Biomarker Analyses

For the analysis of biomarker data, the actual treatment received will be used rather than the treatment assignment at enrollment. Descriptive statistics will be provided for all scheduled post-baseline times of measurement in Study M15-563, with all subjects who were administered a dose in Study M15-563 included. The descriptive statistics will also be provided for the baseline measurement. For subjects whose treatment in Study M15-562 was one of the ABBV-8E12 doses, the baseline value for Study M15-563 will be the baseline value of Study M15-562. For subjects whose treatment in Study M15-562 was placebo, the baseline value will be the last measurement obtained before the first dose of Study M15-563, which might be the last measurement of Study M15-562 as explained in Section 4.2.

Longer-Term Biomarker Data Set: Only data of subjects whose treatment in Study M15-562 was with one of the ABBV-8E12 dose levels will be included in this data set. The data set will include the data for all scheduled times of measurement of Study M15-563. The baseline value for this data set will be the baseline value of Study M15-562.

6.0 Demographics, Baseline Characteristics, Medical History, and Previous/Concomitant Medications

The data analysis will be conducted among treatment groups defined as Studies M15-562/M15-563: 2000/2000 mg, 4000/4000 mg, placebo/2000 mg, and placebo/4000 mg.

